Fibroscan (Echosens, Paris, France) device. A cross-sectional study aiming to define the accuracy of the CAP when compared to liver biopsy found an area under the receiver-operating characteristic (AUROC) curve of 0.81 (0.74-0.88) to identify a degree of \geq 10% of steatosis in the 153 patients studied. Although CAP was not able to accurately tell apart moderate (>33%) from severe (>66%) steatosis, the technique seemed to be more reliable at higher degrees of steatosis, and in patients with no to minimal fibrosis (50% of patients had stage \geq 2 of fibrosis).(2) In a more recent study including 440 paired CAP-liver biopsies the AUROC to identify >33% steatosis with CAP was 0.84 (0.80-0.88),(3) and in a meta-analysis including 1771 subjects it was 0.88 (0.85-0.91).(4) The last study reported positive and negative predictive values of 58% and 94% for the detection of >33% of steatosis (median cut-off point 255 dB/m), and 57% and 93% for the detection of >66% of steatosis (median cut-off point 290 dB/m), respectively.

To date, no study has attempted to study CAP to quantify the degree of liver steatosis in deceased donors. Such study has been largely limited by the fact that only a few institutions have the expertise and resources to operate a Fibroscan. With the development of the Fibroscan 530, a portable TE device, this is no longer a limitation. Given the grave need to increase the number of LT by using EDC allografts, CAP has the potential of becoming a very useful tool during donor assessment (before allocation) by providing a non-invasive and objective evaluation of liver allograft steatosis. If useful, CAP could become quite advantageous to the organ procurement agencies by providing a timely evaluation on steatosis and fibrosis (this from TE), saving resources by avoiding unnecessary liver biopsies and procurement of EDC allografts posing excessive risks to LT recipients (i.e. with excessive steatosis for each given donor-recipient match).

Study Aims

The primary aim of this study is to determine the accuracy of CAP from Fibroscan in the quantification of liver steatosis in donors using liver biopsies as the gold standard. Secondary aims include:

- (1) correlation between TE results and fibrosis
- (2) association of CAP and TE results with post-LT clinical outcomes,
- (3) measurement of change in CAP after LT.

Study Design

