All liver biopsies will be evaluated by two independent liver pathologists blinded to the results of CAP. In all cases, both the snap frozen and formaldehyde liver biopsy specimens will be reviewed and the degree of macrovesicular steatosis graded as per standard recommendations (<5, 5-33%, 34-66%, >66%). Liver pathologists will independently stage fibrosis of liver specimens using the Batts-Ludwig scoring system and the Brunt classification.

Data Analysis

The primary aim is to correlate the CAP results with the degree of hepatic steatosis on the liver biopsy fixed in formaldehyde. Spearman's rho will be used for this analysis. Parallel analyses will be performed with the snap frozen sample, and computerized histomorphometry to determine accuracy of CAP in different possible clinical scenarios. In order to assess whether a threshold value of CAP with a sufficiently high positive predictive value can be defined to obviate the need for a liver biopsy during organ procurement, Receiver Operating Characteristics (ROC) curves will be plotted, and areas under the curve (AUROC) reported as a measure of accuracy of CAP. For this analysis, the magnitude of steatosis in the formaldehyde samples will be dichotomized as \geq 34 or <34% in order to address steatosis as for EDC allografts. A sensitivity analysis using computed histomorphometry results and dichotomizing grading of steatosis as \geq 20 or <20% will be performed in case the prior analysis lacks power, as this degree of steatosis has been found to be associated with poor post-transplant outcomes as well.

Study Title:	Usefulness of Controlled Attenuation Parameter (CAP) for the assessment of liver steatosis
	in liver donors
PI:	[name], MSc, DSc
Institution:	University of Arkansas for Medical Sciences

CAP will be performed with either the M- or XL-probe depending on the skin to liver capsule distance (M-probe if <2.5 cm, and XL-probe when between 2.5 and 3.5 cm) as per manufacturer's recommendations (Echosens, Paris, France).

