The first secondary aim is to examine correlation between TE results and fibrosis stage (Spearman's rho). In addition to correlating the TE results with fibrosis stage, we will explore whether the combination of CAP and TE results can define unacceptability and subsequently help in the decision to discard and organ. To achieve this goal a sensitivity analysis with various combinations of CAP and TE will be tested in logistic regression models, and then cut-off valued determined by constructing AUROC. Agreement between pathologist for both steatosis and fibrosis will be examined with the kappa statistic. A sensitivity analysis for donors on vasoactive amines or a peak ALT or AST >300 before procurement is planned to better determine accuracy of CAP/TE in liver donors.

The second secondary aim is to correlate CAP and TE results with various post-LT outcomes. Various (logistic, linear or proportional hazards) regression analyses will be used depending on the outcome variable of interest (PNF, EAD, retransplantation or death). Predictor variables will include CAP and TE as well as well-known donor and recipient predictors of LT outcomes (i.e. age, MELD, ICU-stay, etc).

The third secondary aim is to determine the change in CAP after LT. Baseline and follow up CAP determinations will be compared with paired t-test or Wilcoxon, depending on distribution of data. Normal distribution will be tested with Shapiro-Wilk. Categorical changes (i.e. \geq 34% to <34%) will be addressed with McNemar's test.

Accurate sample size determination is difficult in this pilot study because the test characteristics are not defined. We propose to examine as many donors as needed to achieve 100 transplanted liver allografts, which will allow detection of meaningful differences between livers with high versus low CAP values. If the prevalence of unacceptably high CAP value is as low as 5% of the livers, the sample size will permit detection of a threshold that has 80% positive predictive value or higher. Between the two participating institutions, it is expected to complete inclusion of 100 transplanted liver allografts in one year. It is expected to include no more than 60 patients at UAMS.

Data Collection and Handling

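### The primary aim is accuracy, but the statistic assigned to it is Spearman's rho; the planned AUROC should be named as the primary measure, with a confidence interval

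*Combined protocol and SAP*

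**What the plan says.** The plan describes its primary aim in three places, in different terms.

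- **Study Aims:** "The primary aim of this study is to determine the accuracy of CAP from Fibroscan in the quantification of liver steatosis in donors", with biopsy as the gold standard. The opening summary agrees.
- **Data Analysis, first paragraph:** "The primary aim is to correlate the CAP results with the degree of hepatic steatosis on the liver biopsy fixed in formaldehyde", followed by "Spearman's rho will be used for this analysis". The pathologists' reading that supplies the reference has four categories, "graded as per standard recommendations (<5, 5-33%, 34-66%, >66"%.
- **Data Analysis, sample-size paragraph:** for 100 transplanted allografts, with as few as 5% having an unacceptably high CAP, "the sample size will permit detection of a threshold that has 80% positive predictive value or higher".

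The first paragraph of Data Analysis also plans ROC curves. Their purpose is to see whether "a threshold value of CAP with a sufficiently high positive predictive value can be defined to obviate the need for a liver biopsy". For this, "the magnitude of steatosis in the formaldehyde samples will be dichotomized as" at least 34% or below 34%, with "areas under the curve (AUROC) reported as a measure of accuracy of CAP". The plan gives this analysis no rank relative to rho, no confidence interval and no target. It gives no significance level, target value or success rule for rho either.

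**The concern.** The primary analysis determines what the study can claim. Rho pools information from every step of the grading scale, including the step between no fat and mild fat. The decision CAP is meant to inform sits at one step, 34%. A test that ranks livers moderately well overall can still be poor at that step.

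If rho is the headline result, a modest but significant value could be reported as the answer to an accuracy question. The plan's only numerical goal, a PPV of 80%, is not linked to rho. The Background justifies the study with published AUROCs of 0.84 and 0.88 for more than 33% steatosis and quotes no correlation, so by the protocol's own usage accuracy means AUROC.

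**Working it through.** **Inputs from the document.** N = 100; reference cut 34%; 5% of livers with high CAP; PPV 80%; published AUROCs 0.84 and 0.88.

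**Assumptions.** Two-sided 0.05 and 80% power (neither is stated); 100 analysable pairs; prevalence of at least 34% steatosis of 5, 10 or 20%.

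**The plan's own figure.** N = 100 cannot be reproduced. The sample-size paragraph gives no significance level, power, comparator or formula, and no figure for rho or AUROC.

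**Step 1: what rho can detect.**
- Critical value: r = t/√(t² + 98) with t = 1.984, giving 0.197.
- Fisher z with the Spearman variance: SE = √(1.06/97) = 0.1045. Detectable rho at 80% power = tanh[(1.960 + 0.842) × 0.1045] = 0.285.
- Power at a true rho of 0.28: atanh(0.28) = 0.2877; 0.2877/0.1045 − 1.960 = 0.79; power = Φ(0.79) = 79%.

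**Step 2: what that rho implies at the 34% cut.** Take CAP and steatosis as bivariate normal with Pearson r = 2 sin(π × 0.28/6) = 0.292. Livers above the (1 − prevalence) quantile of steatosis are the cases. PPV is computed with the same fraction called positive on CAP.

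| Prevalence (assumed) | AUROC | PPV |
|---|---|---|
| 5% | 0.68 | 14% |
| 10% | 0.66 | 21% |
| 20% | 0.64 | 33% |

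The scale here is continuous. On the four grades, with half the livers assumed below 5% steatosis, ties weaken rho: latent r = 0.30 gives rho of about 0.25 and power of 70-74%. At latent r = 0.40, power on the grades is 93-95% while the AUROC is 0.70-0.74. The conclusion is unchanged.

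**Step 3: a check outside that model.** Suppose CAP shifts by 0.8 SD between livers below 5% and livers at or above 5%, and does not distinguish 5-33% from 34% and above. Again let half the livers be below 5%. Simulated trials of 100 then give a significant rho about 95-97% of the time at 5 or 10% prevalence. The AUROC at 34% is about 0.61-0.62, and all of it comes from the contrast with non-fatty livers.

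**Step 4: precision if AUROC is primary.** Hanley-McNeil, with m cases and n = 100 − m non-cases:

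SE² = [A(1 − A) + (m − 1)(Q₁ − A²) + (n − 1)(Q₂ − A²)]/(mn), where Q₁ = A/(2 − A) and Q₂ = 2A²/(1 + A).

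For A = 0.88: A² = 0.7744, Q₁ = 0.7857, Q₂ = 0.8238.

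| Livers ≥34% (assumed) | SE | Approximate 95% CI |
|---|---|---|
| 5 | 0.100 | 0.68-1.00 |
| 10 | 0.072 | 0.74-1.00 |
| 20 | 0.051 | 0.78-0.98 |

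**Step 5: precision of the PPV.** 5% of 100 is 5 CAP-positive livers. An observed 4/5 (80%) has an exact (Clopper-Pearson) 95% CI of 28% to 99.5%.

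**The case against.** The strongest reply is that the accuracy analysis is already in the plan. A reader might infer from the wording of the primary aim that discrimination is not assessed at all. The documents do not support that: the ROC analysis at 34% is in the same paragraph as rho, on the same specimens, and a weak AUROC would be visible beside it. The PPV in the sample-size paragraph also belongs with that threshold question. This narrows the defect to which measure is primary and how it is reported.

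Three other stronger readings also fail.

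- **That the study could formally pass on rho.** The plan sets no significance level or success rule and calls itself a pilot, so there is nothing to pass. Significance here is my convention. What stands is that nothing in the plan prevents a modest rho from being presented as the primary result.
- **That rho is irrelevant to accuracy.** The aim concerns quantification, and CAP is valued in the Background for its continuous scale, so rank correlation across the range has a legitimate supporting role. A high rho is informative: in the model of Step 2, rho of 0.65 gives an AUROC of about 0.88, 0.86 and 0.83 at 5, 10 and 20% prevalence.
- **That the low PPVs are caused by choosing rho.** They mainly reflect rarity. In the same model at 5% prevalence, a CAP with AUROC 0.88 has a PPV of only about 36% when 5% are called positive.

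It is also fair to say that rho uses all 100 livers, whereas the AUROC depends on how many reach 34%. The plan anticipates that the 34% analysis may lack power and holds a 20% cut in reserve. That supports stating the expected interval openly. It does not make rho a measure of accuracy.

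**Conclusion.** The point holds in limited form. Study Aims and Data Analysis describe one primary aim as two different quantities, and the sample size is argued on a third. The measure that the plan itself associates with accuracy has no primary status and no interval.

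A conventionally significant rho at N = 100 is compatible with an AUROC of about 0.64 to 0.68 at the 34% cut, against the 0.84 to 0.88 quoted in the Background. Such a rho would not support a claim of accuracy or of replacing biopsy. These figures rest on an assumed two-sided 0.05 level, a bivariate-normal model on a continuous scale, and an assumed prevalence of 5 to 20%. The direction is the same on the four grades and in the separate check of Step 3. This should be corrected, but the plan does not lack an accuracy analysis.

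**What to change.** 1. Reconcile Study Aims with the first paragraph of Data Analysis. Name the already planned AUROC for at least 34% steatosis on the formaldehyde specimen as the primary accuracy measure, with a 95% CI. Report sensitivity, specificity, PPV and NPV, each with a CI, at the chosen cut-off.
2. Keep Spearman's rho as supporting evidence for quantification across the range of steatosis.
3. Keep N = 100, but replace the PPV sentence in the sample-size paragraph with expected precision: the AUROC intervals in Step 4 for 5, 10 and 20 affected livers, and the 28% to 99.5% interval for a PPV of 4/5.

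**Cost.** Wording only; no new data or procedures. The primary result will look less precise than a correlation p-value, and with few livers at or above 34% the interval will be wide. Renaming the primary measure does not remove that imprecision; it makes it visible before enrolment. Nor does it say how good CAP must be: the sponsor would still need to state what counts as a high enough PPV or AUROC if a claim about avoiding biopsy is intended.

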A database will be created to accumulate all of the clinical information generated during this study. No identifiers, apart from UNOS identification number for donors, and name and DOB for recipients, will be collected. All data will be stored in databases kept in a study folder created at PI's computer (password-protected). Main

Study Title:	Usefulness of Controlled Attenuation Parameter (CAP) for the assessment of liver steatosis
	in liver donors
PI:	[name], MSc, DSc
Institution:	University of Arkansas for Medical Sciences

database will include aforementioned identifiers, however, each pair of subjects (recipient and respective donor) will have a unique study ID assigned, and once an analytic table is created, all PHI will be removed from the table (after approval by the PI). Only this de-identified dataset with unique study ID's will be used for statistical analyses. Therefore, the risk to the privacy of the individuals will be minimized.

The access to the research folder and its contents will be restricted to the research staffs listed in this submission form. The PHI will be kept in the main database for no more than 10 years. The main database containing PHI will be kept in the study folder and will be never transferred out without de-identification of the data. No hard copy research data will be generated in this project.

Each of the participating centers (UAMS and Stanford University) will work independently in gathering their own data. The PI's from each center will share on a monthly basis their subject accrual figures and after study is completed each center will share its de-identified database and a unique database will be built.

Risks and Benefits

TE is a noninvasive procedure and no adverse effects were reported in the registration trials. FDA approval for Fibroscan 502 was obtained in April/2013, and for Fibroscan 530 (the lighter and portable version of Fibroscan 502) in March/2016. CAP received FDA approval in June/2015.

Liver biopsies in an allograft can theoretically result in bleeding, hemobilia, arteriovenous fistulas, or infection in the recipient. However, apart from bleeding, which can be controlled by the transplant surgeon during the surgical procedure, no other complications have been reported. Moreover, liver biopsies are performed routinely during the organ procurement process or by the time of organ implantation, and thus this study would not expose recipients to unusual or unnecessary risks.

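### The PPV at a CAP cut-off chosen in the study's own 100 or so livers, and the AUROC of a selected CAP+TE model, will on average be optimistic, and the plan has no correction

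*Combined protocol and SAP*

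**What the plan says.** All references are to the combined protocol and SAP.

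- **Data Analysis, ROC analysis.** The question is "whether a threshold value of CAP with a sufficiently high positive predictive value can be defined to obviate the need for a liver biopsy". ROC curves are plotted for ≥34% v <34% steatosis on the formaldehyde sample, with "areas under the curve (AUROC) reported as a measure of accuracy of CAP".
- **Data Analysis, first secondary aim.** The team will "explore whether the combination of CAP and TE results can define unacceptability". To do so, "various combinations of CAP and TE will be tested in logistic regression models, and then cut-off valued determined by constructing AUROC".
- **Data Analysis, sample size.** The study examines "as many donors as needed to achieve 100 transplanted liver allografts, which will allow detection of meaningful differences". If as few as 5% of livers have an unacceptably high CAP, "the sample size will permit detection of a threshold that has 80% positive predictive value or higher". The same paragraph calls the study a pilot whose test characteristics are undefined.
- **Data Collection and Handling.** The two centres' data are merged: "after study is completed each center will share its de-identified database and a unique database will be built". Neither centre is held back for validation.
- **Background.** A meta-analysis is cited with positive and negative predictive values of "58% and 94% for the detection of >33% of steatosis (median cut-off point 255 dB/m"), and an AUROC of 0.88. Another study gives 0.84. The analysis does not use the 255 dB/m value.

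The plan names no dB/m value to be tested, no rule for choosing a cut-off, no list of candidate models, no hold-out, cross-validation or bootstrap, and no confidence interval for PPV.

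**The concern.** When a cut-off is chosen because it performs well in a set of livers, and its performance is then reported in the same livers, part of that performance is chance. The same holds for a model picked from several for its AUROC. The direction is predictable: optimistic on average.

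Whether CAP could spare a biopsy turns on PPV at a threshold, and the plan has no step that shows how much of an observed PPV comes from choosing the threshold. Biopsy remains standard of care in this study, so what is at stake is the figure that is published and carried into later work, not the care of participants.

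**Working it through.** **The plan's own figure.** 100 × 5% = 5 livers with high CAP. If 4 of 5 have ≥34% steatosis, PPV is 80% with an exact (Clopper-Pearson) 95% interval of 28–99%. For 5 of 5 the lower limit is 48%. The plan gives no alpha, power, null PPV or interval width, so the claim for N = 100 can be neither reproduced nor refuted. These intervals concern precision, not selection. The 5% is the share of livers with high CAP, not the prevalence of steatosis.

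**Inputs from the documents.** n = 100 (sample-size paragraph); AUROC 0.84 and 0.88 for >33% steatosis (Background).

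**Assumptions, not in the documents.** Prevalence π of ≥34% steatosis of 5, 10, 20 or 30%; equal-variance binormal CAP; two search rules:
- *Youden*: the cut-off that maximises sensitivity + specificity − 1.
- *80% rule*: the lowest cut-off with apparent PPV ≥80%.

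**Formulas.** The separation of the two CAP distributions is d = √2·Φ⁻¹(AUROC), so 1.41 at 0.84 and 1.66 at 0.88. True PPV at cut-off c is π·Φ(d − c) / [π·Φ(d − c) + (1 − π)·Φ(−c)]. Optimism is apparent PPV minus true PPV at the same cut-off, averaged over simulated studies.

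**Results.** Ranges run across the two AUROCs. There were 20,000 simulated studies per scenario, and 5,000 for the SD and the Youden interval row. The bootstrap used 600 studies × 100 resamples, re-selecting the cut-off each time. Results for the 80% rule are among searches that find a cut-off.

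| | π = 5% | 10% | 20% | 30% |
|---|---|---|---|---|
| Youden: apparent PPV, % | 26–31 | 34–40 | 51–56 | 63–68 |
| Youden: true PPV, % | 19–24 | 29–35 | 46–52 | 59–64 |
| Youden: PPV optimism, points | 7 | 5 | 4–5 | 4 |
| Youden: SD of apparent minus true PPV, points | 12 | 10 | 9 | 7 |
| Youden: apparent v true sensitivity, % | 89–92 v 67–70 | 85–88 v 71–74 | 81–85 v 73–76 | 80–84 v 74–77 |
| 80% rule: cut-off found, % of studies | 51–63 | 74–85 | 92–97 | 98–100 |
| 80% rule: PPV optimism, points | 30–39 | 17–24 | 6–10 | 2–4 |
| 80% rule: cut-off flags one liver, % | 48–59 | 22–33 | 4–10 | 1–2 |
| 80% rule, ≥5 flagged: found, % of studies | 5–10 | 27–43 | 72–87 | 92–98 |
| 80% rule, ≥5 flagged: PPV optimism, points | 34–42 | 17–25 | 6–10 | 2–4 |

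**How far an exact interval protects.** The lower 95% limit should exceed the true PPV in at most 2.5% of studies.

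| Lower limit above true PPV, % | π = 5% | 10% | 20% | 30% |
|---|---|---|---|---|
| 80% rule, no minimum flagged | about 2 | about 2 | about 2 | about 2 |
| 80% rule, ≥5 flagged | 10–20 | 3–5 | 2 | 2 |
| Youden | 4 | 4–5 | 4–5 | 4–5 |

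The lower limit reached 80% in essentially no study under any rule.

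**How far a bootstrap correction helps.** Under Youden, corrected PPV still exceeds true PPV by 1–3 points. Under the 80% rule the remaining gap is 24–33 points at 5% prevalence, 9–16 at 10%, 0–3 at 20% and about 0 at 30%. At 5% prevalence and AUROC 0.84, for example, apparent, corrected and true PPV average 0.98, 0.91 and 0.58.

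**CAP+TE.** No size is given, because the plan defines neither the candidate models nor the outcome that counts as unacceptable.

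**The case against.** Much of the opposing case stands.

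- **The committed analyses are sound.** The primary analysis is Spearman's rho, and the accuracy measure the plan promises is the AUROC. A reader might infer that the main result is inflated. It is not: neither rho nor the AUROC of CAP alone involves choosing a cut-off or a model. Neither, however, answers the PPV question that the ROC paragraph poses.
- **It is a pilot.** The plan says so and describes the CAP+TE work as exploratory. A reader might infer that the sponsor means to drop biopsy on the strength of this study; nothing in the documents commits to that. But the label does not remove the bias, and the plan does not say that a derived threshold needs confirmation.
- **The largest figures rest on a rule the plan does not state.** In the plan, 80% is a sample-size statement, not a search rule. At 5% prevalence about half or more of the cut-offs found flag a single liver, which few would take as a usable threshold. With at least 5 flagged, the search usually fails.
- **Under an ordinary rule the PPV bias is small.** Youden PPV optimism is less than its own sampling SD, and apparent PPV reaches 80% in only 1–13% of studies. That comfort covers PPV only; sensitivity is overstated by much more when few livers are steatotic.
- **An exact interval already guards against a false claim of 80%.** Largely true, but the plan does not provide for one.
- **Bootstrap correction fails where the bias is largest.** True, so it should not be the lead remedy.

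**Conclusion.** The concern holds in direction, and its size is conditional. As written, the plan will on average give an optimistic PPV at any study-derived CAP cut-off, an optimistic sensitivity if one is quoted there, and an optimistic AUROC for a selected CAP+TE model.

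Under the stated assumptions, PPV optimism is about 4–7 points with a Youden rule, against a sampling SD of 7–12, and sensitivity optimism is about 6–23 points. If the cut-off were chosen to reach 80% PPV, PPV optimism would be about 30–39 points at 5% prevalence, 17–24 at 10% and 2–10 at 20–30%. A reader might take the 30–39 points as the expected bias of this study. The documents do not support that: they state neither this rule nor any prevalence of ≥34% steatosis.

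Confidence is high for the direction and limited for the size. The point merits a change because a better analysis is available from the same data at little cost.

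**What to change.** 1. **Lead with a fixed cut-off.** Report PPV, NPV, sensitivity and specificity for ≥34% steatosis, with exact intervals, at the 255 dB/m value cited in the Background. State that it does not come from deceased donors, that its cited PPV is 58%, and that it is a selection-free benchmark which does not show whether an 80% threshold exists.
2. **For any study-derived CAP or CAP+TE cut-off**, state one search rule with a minimum number of flagged livers, and list the candidate models. Report the number flagged and the exact interval, noting that the interval ignores the selection. Add optimism-corrected estimates that repeat the cut-off and model selection in each resample, and state that the correction is unreliable when few livers have ≥34% steatosis.
3. **Label such cut-offs exploratory**, needing confirmation in new donors before any conclusion that CAP can replace biopsy.

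The cost is SAP wording and a little programming, with no new data. Reported figures will be less favourable, and the benchmark will be imprecise. The number of livers above 255 dB/m is not given; with PPV near 58%, the exact 95% interval would be 26–88% for 6 of 10 flagged, 36–81% for 12 of 20, and 41–73% for 23 of 40.

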In order to meet the LT demands and to best serve patients, most LT centers are increasingly using marginal donor allografts at risk for poorer outcomes after LT. These so called "extended donor criteria" (EDC) allografts include the use of livers with a high percentage of steatosis, livers derived from older or sicker donors, livers from donors infected with viral hepatitis B or C, and donation after circulatory death (in counterpart to donation after brain death). Although various donor-risk scales have been designed to weigh the consequences of using EDC allografts, none of them provide an accurate risk assessment. Moreover, the trade-off defining the use of EDC allografts is commonly made under far from ideal circumstances (overnight, at facilities with limited resources, with non-specialized on-call personnel), and flawed by subjective evaluations such as determination of the degree of hepatic steatosis.

The percentage of liver steatosis in the donor allograft liver biopsy is of greatest importance to define prognosis of LT, and plays a paramount role in the decision to use or not an allograft. To address this, the amount of large fat droplets (macrosteatosis) within the hepatocyte is semi-quantitatively estimated against the degree of non-fatty liver parenchyma on a given liver biopsy specimen. Although there is controversy as to whether very small lipid droplets (macrosteatosis) should be accounted for in this evaluation, most centers would only consider macrosteatosis in their decision. In general, allografts with >30% of steatosis are more prone to experience primary non-function, early allograft dysfunction, and constitute a risk factor for acute kidney injury, biliary complications, poor allograft survival, and retransplantation.

Controlled-attenuation parameter (CAP) constitutes a non-invasive method of evaluating liver steatosis. It has several advantages over liver biopsy and other methods to assess steatosis in that it is non-invasive, easy to perform, reliable, not expensive, and provides immediate and objective evaluation on a continuous scale. CAP is based on a novel technology measuring the degree of ultrasound attenuation of liver fat from ultrasonic signals acquired during transient elastography (TE) with a

Study Title:	Usefulness of Controlled Attenuation Parameter (CAP) for the assessment of liver steatosis
	in liver donors
PI:	[name], MSc, DSc
Institution:	University of Arkansas for Medical Sciences

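### The 20% steatosis ROC analysis is run only if the 34% analysis lacks power, a trigger the plan leaves undefined, and it changes cut and measurement together

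*Combined protocol and SAP*

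**What the plan says.** All of this is in the combined protocol and SAP.

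- **Primary analysis** (Data Analysis): "The primary aim is to correlate the CAP results with the degree of hepatic steatosis on the liver biopsy fixed in formaldehyde", by Spearman's rho. This needs no cut.
- **Main ROC analysis** (Data Analysis): steatosis in the formaldehyde samples is "dichotomized as \geq 34 or <34% in order to address steatosis as for EDC allografts".
- **Conditional analysis** (Data Analysis): "A sensitivity analysis using computed histomorphometry results" follows, in which "dichotomizing grading of steatosis as \geq 20 or <20% will be performed in case the prior analysis lacks power". The reason given for 20% is that this level has also been linked to poor outcomes after transplantation.
- **Grading** (end of Investigational Approach): two pathologists blinded to CAP read the biopsies, with macrovesicular steatosis "graded as per standard recommendations (<5, 5-33%, 34-66%, >66" percent.
- **Risk level** (Background): in general, "allografts with >30% of steatosis are more prone to experience primary non-function, early allograft dysfunction".
- **Sample size** (end of Data Analysis): "We propose to examine as many donors as needed to achieve 100 transplanted liver allografts".
- **Data pooling** (Data Collection and Handling): the two centers exchange accrual figures monthly and share their de-identified databases after the study is completed.

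**The concern.** A conditional analysis is sound when its condition is written down and can be checked without sight of the result. Here it is neither. Lack of power is not expressed as a number of positive livers, an interval width, a p-value or anything else. The pooled data set exists only after completion, when CAP and histology are both available, and nobody is named as deciding the question blind to CAP. An unwelcome 34% AUROC could therefore prompt a 20% AUROC beside it, while a welcome one would stand alone. A reader of the final report could not tell which had happened.

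The second problem is interpretation. The conditional analysis moves from pathologist grade to histomorphometry and from 34% to 20% in one step. If the two AUROCs differ, the plan gives no way to say whether CAP tracks a digital measurement better or discriminates better at a lower fat level. The ROC work is meant to show whether a CAP threshold could spare donors a biopsy, so that distinction matters.

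**Working it through.** **1. Can the trigger be derived from the plan's own figures?** The sample-size paragraph gives 100 transplanted livers, a 5% prevalence and a positive predictive value of at least 80%. It states no alpha, power or null value, so no formula reproduces the claim. The 5% (0.05 × 100 = 5 livers) is the prevalence of a high CAP value, not of steatosis at 34% or more. The documents give no prevalence for the latter, so 5 and 15 positive livers are used below as an assumed range.

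**2. Precision at the 34% cut.** Take A = 0.88, the meta-analysis AUROC for more than 33% steatosis in Background. The Hanley-McNeil variance is

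[A(1−A) + (n1−1)(Q1−A²) + (n0−1)(Q2−A²)] / (n1·n0), with Q1 = A/(2−A) and Q2 = 2A²/(1+A).

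- Q1 = 0.88/1.12 = 0.7857; Q2 = 1.5488/1.88 = 0.8238; A² = 0.7744; A(1−A) = 0.1056.
- 5 positive, 95 negative: (0.1056 + 4 × 0.0113 + 94 × 0.0494)/475 = 0.0101; SE 0.10; 95% CI about 0.68 to 1.00 (upper limit truncated at 1).
- 15 positive, 85 negative: (0.1056 + 14 × 0.0113 + 84 × 0.0494)/1275 = 0.0035; SE 0.06; 95% CI about 0.76 to 1.00.

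**3. Is that lacking power?** Approximate power is Φ[(A − A0 − 1.96·SE0)/SE], where SE0 is the same formula evaluated at the null A0. With 5 positives, SE0 is 0.133 at A0 = 0.5 and 0.134 at A0 = 0.7.

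- Against 0.5: (0.38 − 0.261)/0.1005 = 1.19, power about 88%.
- Against 0.7: (0.18 − 0.263)/0.1005 = −0.82, power about 21%.
- With 15 positives: above 99% against 0.5, and about 65% against 0.7.

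The same five livers give adequate or inadequate power depending on a null value the plan does not state.

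**4. One possible reading of the trigger.** Suppose, as an assumption only, that lacking power were taken to mean not significant at 0.05. A simulation with no association (100 livers, 10,000 runs per setting, Mann-Whitney test at 34%, then at 20% if the first is not significant) gave a false-positive chance of about 8.0–9.5%, against 4.3–5.2% for the 34% test alone. Assumed ranges were 5–15% prevalence at 34%, 10–30% at 20%, and a correlation of 0.8–1.0 between the two measurements. Two independent tests would give 1 − 0.95² = 9.75%. The plan declares no such test, so this shows what that reading would cost and is not a property of the plan.

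**5. Attribution.** Set the combinations side by side:

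| | Cut 34% | Cut 20% |
|---|---|---|
| Pathologist grade | main ROC analysis | not obtainable from the four grades |
| Histomorphometry | not explicitly planned | conditional analysis |

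The lower-left cell is the bridge. Comparing it with the main analysis isolates the measurement; comparing it with the 20% result isolates the cut. Data Analysis does promise parallel analyses with histomorphometry, but that sentence follows the Spearman analysis and names no cut, so it cannot be relied on to fill the cell.

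**The case against.** A fair defence has four parts.

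- **The 20% analysis is only a sensitivity analysis.** This stands. It is labelled as such and has a clinical reason, and nothing permits dropping the 34% AUROC. A reader might infer that a poor 34% result could be replaced by the 20% one. The text does not support that; the risk is selective supplementing.
- **The target is fixed.** This also stands. A reader might set the more-than-30% figure in Background against the 34% cut and conclude that the steatosis target is undefined. But 34% is prespecified, is a boundary of the grading scale, agrees with the more-than-33% level in the cited CAP studies, and recurs as the example for McNemar's test. The 30% figure is a general background statement. What is missing is a sentence relating the two, since the plan justifies 34% by extended-criteria status and livers at 31–33% fall between them.
- **The trigger could be judged blind.** Power depends largely on the number of livers at 34% or more, and pathologists blinded to CAP produce that count. This is true, and it means that dependence on the result is possible rather than certain. But the plan does not say the count is the criterion or that it will be made without sight of CAP.
- **Changing both features is forced.** A four-grade scale cannot give a 20% cut, so another measurement is needed. That explains the 20% histomorphometry analysis but not the absence of a 34% one beside it.

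**Conclusion.** The concern holds for the conditional clause and for the joint change of cut and measurement. As written, the plan allows the 20% AUROC to be reported or not according to the data, and gives no means of interpreting a difference from the 34% AUROC. The defect is confined to a sensitivity analysis within the ROC work: the Spearman analysis and the prespecified 34% target are untouched.

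Its size cannot be given as one figure. It is tempting to say that the trigger is likely to be met, because the standard error is about 0.10 with 5 positive livers. Without a criterion that does not follow, as the two power values for the same five livers show. Those figures rest on an assumed AUROC of 0.88 and assumed counts of 5 to 15 livers at 34% or more. The change is inexpensive and worth making before the databases are combined.

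**What to change.** In Data Analysis:

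1. State that the main ROC analysis is the AUROC at 34% or more, by pathologist grade on the formaldehyde biopsy.
2. Delete the condition on lack of power. Always report the histomorphometry AUROC at both 20% and 34%, labelled as sensitivity analyses, with confidence intervals and whatever the main result.
3. Add one sentence relating the 34% cut, as a grade boundary, to the more-than-30% risk level in Background. A histomorphometry AUROC at more than 30% is optional. Background describes steatosis as a semi-quantitative estimate on biopsy, so that level may not carry over directly to a computed measurement.

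If the sponsor prefers to keep a condition, define it in advance as a minimum number of livers at 34% or more, counted without access to CAP.

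The cost is a change of wording and one or two extra AUROCs from histomorphometry that is already planned. The drawback is a few more secondary figures to report.
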